#### 9.2.2. Exclusion Criteria

Patients meeting any of the following criteria will not be included in the study:

Exclusion criteria are applied to all treatment and comparator groups unless otherwise noted. Information during the baseline period is used to assess whether a subject meets the criteria unless otherwise noted (see definitions in Section 9.3 Variables). The exclusion criteria will include the following (summarized in Figure 3 above):

- Hysterectomy;
- Endometrial cancer;
- ≥1 prior dispensing of any vaginal estrogen (including study drugs and non-study drugs) prior to the index date for new users of vaginal estrogen. For non-users and E+P HT new users, this criterion will be assessed during the entire baseline period, including the potential index dates.
- $\geq 2$  dispensings of vaginal estrogen drugs on the index date that differ by strength, formulation, or active ingredient.
- Secondary analyses only:
  - $\circ \geq 1$  prior dispensing of E+P HT prior to the index date for new users of E+P HT. For vaginal estrogen users, this criterion will be assessed during the entire baseline period, including the index date;
  - $\circ \geq 1$  prior dispensing of vaginal or non-vaginal progestogen hormone therapy product (single-entity or combination, except contraceptives) not included as E+P HT study drugs.
  - ≥1 dispensing of oral, transdermal, or injectable estrogen hormone therapy product (single-entity or combination, except contraceptives) not included as E+P HT study drugs.

### 9.2.3. Post-Index Period

For new users of vaginal estrogen and E+P HT, the post-index period includes the induction period and the follow-up period. The induction period starts the day after the index date and lasts for six months or until the one of the censoring criteria (below) is met. If a censoring criterion has been met during the induction period, that subject is censored and contributes no follow-up time in the main analysis but may be included in a sensitivity analysis (see Section 9.7.4 Sensitivity Analyses). If no censoring criteria has been met during the six-month induction period, the follow-up period begins on the day after the end of the induction period. Person-time for new users of vaginal estrogen and E+P HT will only be counted during follow-up and only endometrial cancer cases occurring during follow-up will be included in the analysis as cases.

The endometrial cancer incidence rate in non-users is unrelated to treatment so the induction period does not apply to this group. Therefore, follow-up and person-time accrual for non-users begins the

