### 9.1.1. Time Periods

The study period, i.e., the beginning of the baseline period to the end of the follow-up period, is 01 January 2006 (earliest available date) through 31 December 2020 (or most recent available date) in the HIRD, and 01 January 1997 (earliest available date for medical record history) through 31 December 2019 (or most recent available date) in the Swedish registers. The difference between the two data sources in end of study dates is due to the difference in the lag time for populating the HIRD and the Swedish registers.

Ascertainment of exposure and follow-up will be 01 January 2007 - 31 December 2020 (or most recent available date) in the HIRD, and 01 July 2007 - 31 December 2019 (or most recent available date) in the Swedish Registers to allow for a 12- or 24-month baseline period in the HIRD and Swedish data bases, respectively. The index date is the day of initiating a study drug or, for non-users, the date of a gynecological visit that meets all inclusion and exclusion criteria. For new users of vaginal estrogens and E+P HT, a 6-month induction period is allowed following initiation of exposure and prior to beginning follow-up to allow for induction and diagnosis of endometrial cancer (Figure 1). For non-users, follow-up and accrual of person-time starts the day after the index date. The unexposed period before a woman starts any vaginal estrogen will be included as time at risk for a non-user until they begin using one of these drugs. The unexposed time at risk (non-users) will be censored if and when they start using vaginal estrogen, E+PHT or other non-study estrogen or progestogen medications. A sensitivity analysis is included that varies the length of the induction period and includes an induction period for the non-user cohort. Table 1 summarizes the different time periods for the two data sources. Patients may differ in their follow-up dates depending on when they meet the study inclusion, exclusion, and censoring criteria.

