# 9.2.1. Inclusion Criteria

Patients must meet all of the following inclusion criteria to be eligible for inclusion in the study:

1. Women must have  $\geq 1$  study drug dispensing, or  $\geq 1$  gynecological visit, that meets each of the following criteria to be eligible for inclusion in a study cohort (Figure 3; for additional details on study drugs and gynecological visits, see Section 9.3 Variables):

• ≥1 dispensing of vaginal estrogen not indicated for severe vasomotor symptoms or any E+P HT, or a gynecological visit for non-users, from 01 January 2007 through 31 December 2020 (or most recent available date) in the HIRD, and 01 July 2007 – 31 December 2019 (or most recent available date) in Sweden (see Annex 1: Appendix B and Appendix F for vaginal estrogen and E+P HT medications)

Vaginal estrogen: Vaginal estrogen drugs include products which are approved only for one or more symptoms of vulvar and vaginal atrophy due to menopause. Thus, Femring (estradiol acetate vaginal) and Ogen (estropipate vaginal) which are also indicated for moderate to severe vasomotor symptoms, are not included as study drugs. Estrace (estradiol cream) is also excluded due to its indication for vasomotor symptoms and its high concentration of estradiol resulting in greater systemic absorption. Vaginal estrogen study drugs include the following products:

HIRD: Estring, Vagifem, Yuvafem, Imvexxy, generic estradiol (tablet), and Premarin VC;

Sweden: Oestring and Vagifem.

E+P HT: oral, transdermal, or injectable estrogen-progestogen combination hormone therapy products.

Gynecological visit: outpatient office visit with provider specialty of gynecology, or diagnosis/procedural codes for gynecological exam or Pap smear.

2. Female aged  $\geq$ 50 years on the first study drug dispensing date or on the gynecological visit date for non-users (the index date).

3. Minimum required baseline observation period:

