#### 9.7.3.1. Primary Analysis

The primary analyses will estimate and compare the IR of endometrial cancer in postmenopausal women aged  $\geq 50$  years with a uterus regardless of prior use of hormone therapy in the following PS matched cohorts: (Annex 1: Table 5).

- a. New users of LDVE versus non-users of vaginal estrogen.
- b. New users of MDVE versus non-users of vaginal estrogen.
- c. New users of HDVC versus non-users of vaginal estrogen (HIRD only).

Person-time for treatment groups will begin after a six-month induction period and include any subsequent follow-up time until a censoring event occurs. Person-time for non-users will begin the day after their index date and continue until a censoring event.

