# 9.7.4. Sensitivity Analyses

Several sensitivity analyses will be conducted. Results from analyses conducted in the HIRD and Sweden will be pooled.

- HIRD and Sweden: The impact of various induction periods on the HR estimates will be assessed by calculating IRs and HRs for LDVE users and nonusers using no induction period, and an induction period of 3 months (lagging the start of follow-up for the LDVE group), and 12 months (Annex 1: Table 7 and 12). Additionally, the impact of lagging the start of follow-up for the non-user group will be assessed. LDVE users will be compared to nonusers with a six-month induction period for both groups.
- 2. HIRD and Sweden: To evaluate the possibility of informed censoring and selection in the main analysis resulting from the inclusion of multiple treatment episodes, a sensitivity analysis restricting follow-up to the first treatment episode will be conducted (Annex 1: Table 8 and 12). The HR of endometrial cancer will be calculated implementing censoring upon restart of index drug. The rationale is that the decision about whether or not to restart treatment could be influenced by past treatment experience. The comparison will be done for the following cohorts:
  - a. LDVE users versus non-users.
  - b. MDVE users versus non-users.
  - c. HDVC users versus non-users (HIRD only).
  - d. LDVE new users versus E+P HT new users.
  - e. MDVE new users versus E+P HT new users.
  - f. HDVC new users versus E+P HT new users (HIRD only).
- 3. HIRD and Sweden: An intent-to-treat (ITT) analysis will be conducted for the possibility of informed censoring and selection in the main analysis resulting from censoring on switching treatment. The ITT analysis will consider patients at risk during the entirety of their follow-up, regardless of discontinuing, or switching treatment, until the earliest of a diagnosis of endometrial cancer, a hysterectomy procedure, health plan disenrollment (HIRD only), emigration (Sweden only), death, or end of study. The HRs will be calculated comparing LDVE users to non-users, and, if sample sizes allow, stratified by prior use of hormone therapy. (Annex 1: Table 8 and 12).

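### In the primary comparisons exposed women are followed only after a 6-month lag but non-users from the day after a gynecological visit, so cancers under work-up at index can count only against non-users

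*Protocol*

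**What the plan says.** **Exposed women.** Under section 9.2.3 the induction period starts the day after index and "lasts for six months or until the one of the censoring criteria (below) is met". Endometrial cancer is one of those criteria. A woman who meets one in the lag contributes no follow-up to the main analysis, and "only endometrial cancer cases occurring during follow-up will be included in the analysis as cases".

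**Non-users.** Section 9.1.1: "For non-users, follow-up and accrual of person-time starts the day after the index date". Section 9.7.3.1 repeats this for the primary analysis: "Person-time for non-users will begin the day after their index date and continue until a censoring event". Table 1 agrees. Section 9.2.3 gives the reason: "The endometrial cancer incidence rate in non-users is unrelated to treatment so the induction period does not apply to this group".

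**Purpose of the lag.** Section 9.1.1 places it "prior to beginning follow-up to allow for induction and diagnosis of endometrial cancer". That is two purposes, not one.

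**The non-user index event.** Section 9.2.1 defines it as an "outpatient office visit with provider specialty of gynecology, or diagnosis/procedural codes for gynecological exam or Pap smear". Visits for symptoms are not excluded. In Sweden, section 9.3.1 takes these visits from specialist outpatient care.

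**What is removed at baseline.** Section 9.2.2 and Table 1 exclude cancers recorded up to and including the index date. Annex 2, section 4.1, dates a HIRD case at the first encounter carrying a qualifying code.

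**Symmetric lag.** Section 9.7.4, item 1, plans it as a sensitivity analysis: "LDVE users will be compared to nonusers with a six-month induction period for both groups". MDVE and HDVC have no such analysis.

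**The concern.** The stated reason covers only half of what the lag does. It is true that a non-user has no drug induction to wait for. But the lag also removes cancers that were already present or being investigated at index, and non-users can have those too. They enter the cohort at a gynecological encounter. A woman investigated at that visit and coded some weeks later passes the baseline exclusion and becomes an incident non-user case. The same sequence in an exposed woman falls inside the lag and is dropped.

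In Sweden the contrast may be sharper. Section 9.9.2 says investigation should precede vaginal treatment, so exposed women would tend to be investigated before index and then lagged as well.

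This is a safety study required by a regulator. If diagnoses do cluster after the index visit, the error runs toward no harm in all three primary comparisons with non-users, and it passes into the pooled LDVE and MDVE estimates of section 9.7.5. The large sample gives no protection, because this is bias and not random error.

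**Working it through.** **The plan's own figure.** Section 9.5.1 uses HR 1.5, a 1:4 ratio, α = 0.05 and 80% power. Taken as two-sided, the required events are (1.960 + 0.842)² / (0.2 × 0.8 × (ln 1.5)²) = 298.4, rounded up to 299 = 60 + 239, as stated. The exposed sample is 298.4 × 0.2 / 0.000745 / 2.4 = 33,377, also as stated. The sample size calculation is sound; the issue is where follow-up starts.

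**Inputs for the bias.** Median follow-up is 2.4 years and the background rate 74.5 per 100,000 person-years (section 9.5.1). *Assumption, not in the protocol:* the non-user rate in months 0–6 is k times the later rate. The Cox clock is taken to start at the start of follow-up.

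**Formula.** If a share s of non-user person-time falls in the first 6 months, the non-user rate is inflated by 1 + s(k − 1), and the observed HR is the true HR divided by that factor.

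- Follow-up fixed at 2.4 years: s = 0.5/2.4 = 0.208.
- Exponential follow-up with median 2.4 years: s = 1 − exp(−0.5 × ln 2/2.4) = 0.134.

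| k | Inflation (fixed / exponential) | True HR 1.5 reads | True HR 1.0 reads |
|---|---|---|---|
| 0.5 | 0.90 / 0.93 | 1.67 / 1.61 | 1.12 / 1.07 |
| 1 | 1.00 / 1.00 | 1.50 / 1.50 | 1.00 / 1.00 |
| 2 | 1.21 / 1.13 | 1.24 / 1.32 | 0.83 / 0.88 |
| 3 | 1.42 / 1.27 | 1.06 / 1.18 | 0.71 / 0.79 |
| 5 | 1.83 / 1.54 | 0.82 / 0.98 | 0.55 / 0.65 |

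**The same in absolute terms, fixed follow-up.** Background risk over 2.4 years is 74.5 × 2.4 = 178.8 per 100,000. Half of that, about 89 extra early diagnoses per 100,000 non-users (0.09%), would make a true HR of 1.5 read 1.0.

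**Simulation check.** Cox models were fitted to 40 simulated data sets per setting, at the HIRD sizes of 152,941 and 611,764, with exponential follow-up and a true HR of 1.5. The geometric mean HRs were:

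| k | One-sided lag, clock from start of follow-up | One-sided lag, clock from index with delayed entry | 6-month lag in both groups |
|---|---|---|---|
| 2 | 1.32 | 1.50 | 1.50 |
| 3 | 1.19 | 1.50 | 1.50 |
| 5 | 0.97 | 1.51 | 1.51 |

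With time since index and delayed entry, early non-user events meet no exposed woman in the risk set, so the HR is protected. The non-user incidence rate stays inflated under either clock.

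**The case against.** **The issue is recognised and tested.** Item 1 of section 9.7.4 includes an analysis with no lag and one with 6 months in both groups, in both databases, for LDVE, the exposure named in the study title. This stands in part. Those analyses could reveal the problem for LDVE, but they would leave the primary and pooled estimates unchanged, and they do not cover MDVE or HDVC.

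**Direction and size are not known.** A reader might infer that the primary HR is biased downward as a matter of fact. The protocol does not support that. It gives no k; the qualifying visits include routine exams and Pap smears; and cancers coded up to the index date are excluded. If early diagnoses were fewer than later ones, the bias would reverse. This stands: downward is likely, not established.

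**The Cox time axis is not stated.** It may properly be left to the SAP. Table 1 and section 9.7.3.1 read more naturally as a clock starting with follow-up, but an index clock with delayed entry would protect the HR. This stands for the HR. It does not rescue the incidence rates, which the primary objectives also set out to estimate and compare.

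**2.4 years is a median.** Treating it as everyone's follow-up gives the larger bias; hence the two figures for each k.

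**Matching.** A reader might also infer that the lag undoes the propensity score match, since an exposed woman who refills systemic hormone therapy within 6 months contributes nothing while a similar non-user contributes from day 1. But the non-user is also censored at her next hormone dispensing, and matching details are deferred to the SAP. Any effect on balance, or on the prior-therapy strata of Objective 2, is secondary and unquantified.

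**Conclusion.** The asymmetry is explicit, and the reason given for it does not cover the diagnostic purpose that section 9.1.1 assigns to the lag. Early cancers are removed from one side of the comparison only. If k > 1, the non-user incidence rate is too high whichever clock is used, and with a clock from the start of follow-up the HR is too low: 1.24–1.32, 1.06–1.18 or 0.82–0.98 in place of 1.5 for k = 2, 3 or 5. These are ranges under an assumed k, not estimates of the actual bias.

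It would be wrong to call this immortal-time bias. Exposed women lose both events and person-time during the lag; the fault is that early diagnoses are removed from one group and not the other.

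The primary analysis should be changed, because the bias would probably favour no harm and is cheap to remove.

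**What to change.** In sections 9.1.1, 9.2.3 and 9.7.3.1, Table 1 and Figure 1, start follow-up 6 months after index in both groups for LDVE, MDVE and HDVC versus non-users. Include only women still at risk at that point, and bring the abstract into line. Check covariate balance in the women actually analysed; re-matching at 6 months is optional. In section 9.7.4, item 1, keep the one-sided lag as the sensitivity analysis.

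**Cost in HIRD, LDVE.** Expected non-user events fall from 611,764 × 2.4 × 0.000745 = 1,094 to 611,764 × 1.9 × 0.000745 = 866. Exposed women are already lagged, so their expected events at the background rate, 152,941 × 2.4 × 0.000745 = 273, do not change. The SE of the log HR goes from √(1/273 + 1/1,094) = 0.0676 to √(1/273 + 1/866) = 0.0694, about 3% larger. If the 2.4 years already include the exposed lag, the increase is about 2%. Power for HR 1.5 stays above 99%: ln 1.5 / 0.0694 = 5.8, against a critical value of 1.96.

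The target population also narrows slightly: non-users must remain enrolled, uncensored and cancer-free for 6 months, a condition the exposed women already have to meet.

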### PFIZER CONFIDENTIAL

day after their index date (i.e., the date of a gynecological visit that meets all inclusion and exclusion criteria). Follow-up for all subjects will extend through the earliest of the following censoring events:

- Hysterectomy;
- Endometrial cancer;
- Dispensing of an estrogen hormone therapy product not included as a study drug (single-entity or combination, vaginal or non-vaginal formulation)
- Dispensing of a progestogen hormone therapy product not included as E+P HT (single-entity or combination, vaginal or non-vaginal formulation);
- End of continuous health plan eligibility (HIRD only);
- Emigration from Sweden (Sweden only);
- Death;
- End of the study period.
- Dispensing of a study drug that is in a different treatment group than the index treatment group, i.e., switching between LDVE, MDVE, HDVC, or E+P HT treatment groups;

Additional censoring criteria for non-users only:

• Dispensing of any study drug, which are defined in Section 9.2.1 Inclusion Criteria.

#### 9.3. Variables

In the HIRD, diagnoses and procedures for both outpatient and inpatient visits are identified by International Classification of Diseases, Nineth Revision, Clinical Modification (ICD-9-CM) and International Classification of Diseases, Tenth Revision, Clinical Modification (ICD-10-CM) diagnostic and procedure codes, Current Procedural Terminology (CPT) codes, and Healthcare Common Procedure Coding System (HCPCS) codes. Outpatient pharmacy claims are captured by National Drug Codes, which can then be translated to broader categories of coding such as Generic Product Identifier (GPI) codes that correspond to the generic drug subclass level of resolution. Specific codes used to generate the variables of interest are provided in Annex 1: Appendices B-D.

In the Swedish National Patient Register (NPR), inpatient and outpatient hospital diagnoses will be identified using ICD-10-Sweden (SE) codes and procedures will be identified using Swedish procedure codes (Klassifikation av vårdåtgärder) (Swedish for "Classification of Healthcare Measures"), and Nordic Medico-Statistical Committee procedure codes. Exposure to drugs will be identified from the Swedish SPDR using Anatomical Therapeutic Chemical (ATC) codes and information on dispensing date, package size, product name, dispensed amount of drug, drug strength, defined daily dose, and drug formulation. Endometrial cancer will be ascertained from the Swedish Cancer Register using information on tumor location coded to ICD-O-2/3. PFIZER CONFIDENTIAL

CT24-WI-GL02-RF023.0 Non-Interventional Study Protocol Template For Secondary Data Collection Study 20-May-2021

Page 28

### 9.3.1. Exposures, Comparators, and Treatment Episodes

GPI codes will be used to identify vaginal estrogen and E+P HT products in the HIRD, (Annex 1: Appendix B) and ATC codes, formulation, brand name, and strength will be used to identify vaginal estrogen and E+P HT Swedish products (Annex 1: Appendix F). Gynecological visits for non-users will be identified in the HIRD using ICD-9-CM and ICD-10-CM diagnostic codes, HCPCS codes for annual exams, CPT codes for pap smear procedures, and physician's specialty code (Annex 1: Appendix C). Gynecological visits will be captured as non-primary outpatient care in the Swedish NPR. Proxies for gynecological visits (i.e., related procedure codes, specialist encounters, and/or reimbursement) will be considered, as appropriate.

Treatment episodes (Annex 1: Appendix I) will be created based on segments of continuous use among the study drug treatment groups, i.e., LDVE, MDVE, HDVC, and E+P HT. Continuous use is defined as consecutive drug dispensings for a treatment group, with no more than 90 days between the end of the days' supply of the earlier prescription and the dispensing date of the next prescription. In order to determine exposure status for vaginal estrogen users during the treatment episode, daily dose must first be computed for each prescription starting with the index dispensing. In the HIRD, daily dose for vaginal estrogen dispensings will be calculated as the drug strength dispensed multiplied by the drug quantity and divided by the days' supply. In Sweden, days' supply is not directly available from the SPDR. Thus, days' supply and daily dose will be estimated for each dispensed vaginal estrogen prescription based on assumptions such as defined daily dose and duration for use. For the E+P HT comparator group, dispensed amount of drug, drug strength and defined daily dose will be used to construct treatment episodes of continuous use. Exposure definitions will be further detailed in the statistical analysis plan (SAP).

The prescription daily doses of the vaginal estrogen dispensings will then be categorized as follows:

- LDVE: <10 mcg/day estradiol or <0.3 mg/day conjugated estrogen;
- MDVE: >10 25 mcg/day estradiol or >0.3 0.45 mg/day conjugated estrogen;
- HDVC: >0.45 mg/day conjugated estrogen.

Vaginal estrogen users will enter the exposure group corresponding to the dose of their first study drug dispensing. Women whose first dispensing was E+P HT will enter the E+P HT comparator group. If a vaginal estrogen user changes dose categories or switches to E+P HT, she will be censored on the dispensing date of the new prescription. Similarly, if an E+P HT user switches to vaginal estrogen use, she will be censored on the vaginal estrogen dispensing date.

Patients may use different products and strengths for study drugs within their treatment group. If there are overlapping prescriptions for different products within the same treatment group, then it will be assumed that the patient stopped taking the first prescription drug and started the second prescription drug on the day it was dispensed (no stockpiling). If the patient has overlapping prescriptions for the same drug and dose, the prescriptions will be stockpiled, i.e., the overlapping days from the second prescription will be added to the end of the days' supply of the first

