#### PFIZER CONFIDENTIAL

01 July 2007 to 31 December 2019 (or most recent available date) in the Swedish National Registers (the exposure ascertainment period). Similarly, two additional exposure groups will be created for MDVE (daily doses >10 mcg – 25 mcg/day estradiol or >0.3 mg – 0.45 mg/day conjugated estrogen) and, in the HIRD only, HDVC (daily doses >0.45 mg/day conjugated estrogen). These two additional groups will also include women with  $\geq$ 1 dispensing of MDVE or HDVC, respectively, regardless of prior use of hormone therapy. The difference in study periods between the HIRD and Swedish databases is due to the difference in lag time for data availability between the two data sources. The comparator groups are: (1) women with  $\geq$ 1 gynecological visit (i.e., non-users) and (2) new users of E+P HT with no prior use of hormone therapy. Women with less than 12 months of continuous health plan enrollment in the HIRD or less than 24 months of medical history in Sweden prior to the index date, without a uterus, or with a history of endometrial cancer will be excluded.

**Variables:** Vaginal estrogen use will be determined using prescription drug codes from pharmacy claims and dispensings. Diagnosis of endometrial cancer will be identified in the HIRD using codes that have been validated in the HIRD, and in Sweden using records in the Swedish Cancer Register. Covariates will include patient demographics, comorbidities, medications, and healthcare utilization. A listing of study variables is provided in Section 9.3 Variables.

**Data Sources:** The HIRD is a longitudinally integrated research database comprising automated payment claims for healthcare encounters since 01 January 2006 from included health insurance plans across the US. It is among the largest of its kind in the US, with current enrollment of approximately 70 million members as of 2018. The HIRD has been extensively used for pharmacoepidemiologic research, including many post approval safety studies. The HIRD includes enrollment data, medical care, physician specialty, laboratory results (one third of patients), prescription drug use, and healthcare utilization that can be tracked for each individual throughout the course of their enrollment.

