The United States (US) Food and Drug Administration (FDA) has issued a post-marketing requirement (PMR) to each Marketing Authorizations Holder (MAH) of an LDVE for an observational study to evaluate the rate of endometrial cancer among postmenopausal women with a uterus who use LDVE unopposed by a progestogen. Pfizer is the MAH for Estring® 2 mg (vaginal ring, 7.5 mcg/24 hours) and Premarin® Vaginal Cream 0.625 mg/gram (Premarin VC) and received a PMR notification for each product. Premarin VC has a higher estrogen concentration but is indicated for both low-dose and high-dose treatment regimens. In order to address the safety concerns for Premarin VC set forth in the PMRs, Pfizer includes Premarin VC in this study, with high-dose regimens evaluated as a separate exposure group. Analyses including Premarin VC will only be conducted in the HealthCore Integrated Research DatabaseSM (HIRD) as Premarin VC is not marketed in Sweden. A comprehensive feasibility assessment (submitted to the FDA on 28 June 2018) was conducted to ensure a scientifically valid observational study could be successfully executed using the HealthCore Integrated Research DatabaseSM (HIRD). This protocol describes the non-interventional study that will be conducted in the US and Sweden to fulfill the PMR commitment to the FDA to assess endometrial cancer risk among users of LDVE. Sweden was specifically requested by the FDA in order to fulfill this PMR. This non-interventional study is designated as a Post-Authorization Safety Study (PASS) and is a post-marketing commitment to the FDA.

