### **Figure 2: Study Population**

Abbreviations: E+P HT, estrogen-progestogen combination hormone therapy; HDVC, high-dose Premarin VC (HIRD only); HIRD, HealthCore Integrated Research Database; LDVE, low-dose vaginal estrogen; MDVE, moderate-dose vaginal estrogen.

Note: Bolded boxes outlined in blue indicate an exposure or comparator group.

The three vaginal estrogen exposure groups and the two comparator groups are described below and summarized in Figure 2 (for definitions of study drugs and gynecological visits, see Section 9.2 Setting and Section 9.3 Variables):

- Exposure 1: New Users of LDVE.
  - o Women who had ≥1 dispensing of an LDVE during the exposure ascertainment period with prescription daily doses ≤10 mcg estradiol or ≤0.3 mg conjugated estrogen at cohort entry and no prior dispensings of vaginal estrogen. Low-dose Premarin VC (HIRD only) is defined as 0.5 g/day dose (equal to daily average strength 0.3 mg or less conjugated estrogens. It should be noted that these women may or may not have used hormone therapy prior to the index date and will be included regardless of such prior use.
- Exposure 2: New Users of MDVE.
  - Women who had ≥1 dispensing of a MDVE during the exposure ascertainment period with prescription daily doses >10 mcg 25 mcg estradiol or >0.3 mg 0.45 mg conjugated estrogen at cohort entry and no prior dispensings of vaginal estrogen. It should be noted that these women may or may not have used hormone therapy prior to the index date and will be included regardless of such prior use. The Swedish cohort will only include subjects with ≥ 1 dispensing of 25mcg estradiol (Vagifem).
- Exposure 3: New Users of HDVC (HIRD Only).
  - Women who had ≥1 dispensing of Premarin VC during the exposure ascertainment period with prescription daily doses >0.45 mg conjugated estrogen at cohort entry and no prior dispensings of vaginal estrogen. It should be noted that these women may or may not have used hormone therapy prior to the index date and will be included regardless of such prior use.
- Primary Comparator: Non-users of vaginal estrogen.
  - Women who had  $\geq 1$  gynecological visit during the exposure ascertainment period, and no dispensings of vaginal estrogen prior to or on the gynecological visit. It should be noted that these women may or may not have used hormone therapy prior to the index date and will be included regardless of such prior use.

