#### 9.9.2. Swedish Registers, Sweden

In the Swedish registers, entry is upon birth or immigration to Sweden and exit from the registers is upon emigration or death.

The Swedish registers used to identify vaginal estrogen use do not have information on daily dose. As a result, when a patient is given a prescription of a known number of vaginal estrogen tablets at a given strength per tablet, it is not clear whether they are to take one or more tablets per day. To determine the length of a treatment episode and the dosage category (LDVE or MDVE), it is assumed that patients are prescribed vaginal estrogen according to the recommended daily dosages. All vaginal estrogens under study available in Sweden are recommended to be used within the low-dose range except for Vagifem, which was available at a MDVE strength per tablet for a limited

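### The HIRD daily-dose formula has no rule for vaginal rings: taking strength as 2 mg, it puts Estring above the low-dose limit whenever the days' supply is under 200 days per ring

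*Protocol*

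**What the plan says.** Section 9.3.1 says that in the HIRD the daily dose of a vaginal estrogen dispensing "will be calculated as the drug strength dispensed multiplied by the drug quantity and divided by the days' supply". No product or formulation is exempted. The same section makes the result decisive in two ways. At entry, "Vaginal estrogen users will enter the exposure group corresponding to the dose of their first study drug dispensing". During follow-up, "If a vaginal estrogen user changes dose categories", she is censored on the date of the new dispensing.

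The estradiol limits are at most 10 mcg/day for LDVE and, for MDVE, "daily doses >10 mcg – 25 mcg/day estradiol" (Section 4, Study Population; also Section 9.1.2). HDVC is defined for conjugated estrogen only, so no group exists for estradiol above 25 mcg/day.

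Estring is a HIRD study drug (Section 9.2.1). Section 7 lists it as "2 mg (vaginal ring, 7.5 mcg/24 hours") and names it as one of the two sponsor products that received a post-marketing requirement as an LDVE.

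Sweden is handled differently. The study products are "Sweden: Oestring and Vagifem" (Section 9.2.1). Section 9.9.2 assumes recommended dosing and states: "All vaginal estrogens under study available in Sweden are recommended to be used within the low-dose range except for Vagifem". The Swedish MDVE group is limited to 25 mcg Vagifem (Section 9.1.2, the sentence starting "The Swedish cohort will only include subjects with").

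**The concern.** Strength times quantity over days' supply is an average daily dose only when everything dispensed is used within that period. That is reasonable for tablets, inserts and cream. A ring releases at a fixed rate and may be replaced with much of its content still inside, so content over time is not the dose received.

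Because group membership is read from this number, the error would not stay in a descriptive column. Ring users could leave the LDVE versus non-user comparison, although Estring is one of the products the study exists to assess. They could enter MDVE while receiving 7.5 mcg per 24 hours, or match no group at all. The ring stratum within LDVE (primary objective 3, by formulation) would lose its Estring users. A woman moving from a low-dose product to the ring would be censored as if her dose category had changed. LDVE and MDVE would also mean different things in the HIRD and in Sweden before Section 9.7.5 pools their hazard ratios.

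**Working it through.** **Inputs**
- Formula: strength × quantity / days' supply (Section 9.3.1).
- Ring content 2 mg = 2,000 mcg; release rate 7.5 mcg/24 h (Section 7).
- LDVE limit 10 mcg/day; MDVE upper limit 25 mcg/day (Sections 4 and 9.1.2).
- Days' supply per ring, *d*: not given. Treated as a range; 90 days is used only as an illustration.
- Meaning of strength for a ring: not stated. Both readings are tried.

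**The figure the formula should return** is the protocol's own 7.5 mcg/day.

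**Reading (a): strength is the 2 mg content, one ring.** Daily dose = 2,000 / *d* mcg.
- Equals 7.5 at *d* = 2,000 / 7.5 = 266.7 days, the time needed to release the whole 2 mg at the stated rate.
- Equals 10 at *d* = 2,000 / 10 = 200 days.
- Equals 25 at *d* = 2,000 / 25 = 80 days.

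| Days' supply per ring | Derived dose (mcg/day) | Group assigned |
|---|---|---|
| 30 | 66.7 | none for estradiol |
| 60 | 33.3 | none for estradiol |
| 80 | 25.0 | MDVE |
| 90 | 22.2 | MDVE |
| 120 | 16.7 | MDVE |
| 180 | 11.1 | MDVE |
| 199 | 10.05 | MDVE |
| 200 | 10.0 | LDVE |
| 267 | 7.5 | LDVE |

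Across 80 to 200 days the derived dose is 25.0 / 7.5 = 3.3 down to 10.0 / 7.5 = 1.3 times the stated rate. At an assumed 90 days it is 22.2 / 7.5 = 3.0 times; at 7.5 mcg/24 h the ring would have delivered 7.5 × 90 = 675 of its 2,000 mcg. Two rings over 180 days give 4,000 / 180 = 22.2, so the limits are days per ring.

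**Reading (b): strength is 7.5 mcg.** Daily dose = 7.5 / *d*. At an assumed 90 days this is 0.083 mcg/day, 90 times below the stated rate. It still falls in LDVE.

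The formula therefore returns 7.5 mcg/day under neither reading, except at about 267 days under (a). Only reading (a) with fewer than 200 days per ring changes the group.

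**Comparison with Sweden.** Section 9.9.2 places Oestring in the low-dose range by assumption, and 25 mcg Vagifem is the only Swedish MDVE product. Under reading (a) with less than 200 days, the HIRD would place its ring elsewhere.

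**The case against.** The strongest reply is that this is detail for the SAP. The paragraph holding the formula leaves further exposure definitions to that document, and Section 9.7 lets the SAP modify the protocol's plans. The drug and code lists in Annex 1 (Appendices A and B) and the episode figures (Appendix I) are also separate documents, and any of them might fix how the ring is coded. This limits the practical consequence, and the absence of a ring rule is shown only for the protocol text. It does not remove the problem: the protocol does not leave the ring's dose open, it prescribes a calculation that is wrong for a named study drug. A SAP that follows it inherits the error, and one that corrects it departs from the protocol.

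Second, misclassification needs two facts the protocol does not supply: strength recorded as 2 mg, and fewer than 200 days' supply per ring. That stands, and the conclusion is conditional on both. The 2 mg reading is the natural one, since the protocol's product listing gives Estring as 2 mg without its release rate.

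Third, reading (b) does no harm to group assignment. That is correct. The dose only sorts women into groups, and the listed strata use episode days, dispensings, formulation and ingredient. Under (b) the number is wrong but no comparison changes.

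Fourth, the intended class is plain, and programming checks (Section 9.8.1) and the tabulation of formulation by group could expose rings sitting in MDVE. They might, but none of those checks names rings, and a check against the protocol's formula would pass.

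**Conclusion.** The rule is wrong as written for rings and should be corrected. On the protocol's own listed strength of 2 mg, Estring exceeds the LDVE limit for any days' supply under 200 days per ring: MDVE from 80 to under 200 days, no estradiol group below 80. This contradicts the 7.5 mcg/24 h stated in Section 7 and the low-dose placement of the ring in Sweden.

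The direction of the damage should be stated accurately. LDVE would lose a product, not gain higher-dose users; it would still hold low-dose tablets, inserts and low-dose Premarin VC. The contamination would be in MDVE, from women receiving a low dose.

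The conclusion assumes that strength is the ring's content and that ring claims carry fewer than 200 days per ring. The size of any effect on the hazard ratios cannot be derived, because the number of HIRD ring users is not given. Confidence is medium for that reason; the arithmetic itself is exact.

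**What to change.** Add one sentence to Section 9.3.1: for vaginal rings the daily dose is the stated release rate (7.5 mcg/24 h for Estring, hence LDVE), and days' supply is used only for episode length. Keep the existing formula for tablets, inserts and cream. Every Estring dispensing then falls in LDVE whatever its days' supply or strength coding.

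Before cohorts are built, run one test dispensing for each product listed in Section 9.2.1. Confirm that the derived group is the intended one and that the HIRD and Sweden agree.

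The cost is that sentence, one line of exposure code and a short test. No new data are needed.
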